1 OBJECTIVES

1.1 Study Objectives

1.1.1 Primary Objectives

- To determine the impact of a chemokine-modulatory regimen on the immune microenvironment of colorectal liver metastases, specifically the changes in the ratio between CTL marker (CD8a gene expression) to Treg markers (FoxP3 gene expression)

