8 STUDY ENDPOINTS

8.1 Primary Endpoint

- Immunologic efficacy will be assessed by the increase in the total number of tumor-infiltrating CD8+ T cells in the CRC lesions (measured as the ratio between the CD8 mRNA message and the expression of the housekeeping gene HPRT which will be provided by the study statistician in a SAS compatible excel formatted electronic file), and comparing the total number of tumor-infiltrating CD8+ T cells in pre-treatment vs post-treatment biopsies.

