11.3 Pathology

Fresh Biopsy Samples

At each liver biopsy collection time point, 6 total cores will be obtained, including at least 5 tumor cores and 1 additional core of surrounding liver tissue (to enhance the stringency of our assays). 4 cores of tumor and 1 core of surrounding liver tissue will be placed in Dulbecco's Phosphate-Buffered saline, and 1 core of tumor will be placed in formalin, and processed to FFPE block per institute standard.

Pre- and post-treatment cores should be obtained from the same lesion. If non-necrotic lesions are present at baseline, they should be prioritized for biopsy, with the necrotic lesions being

PROTOCOL TITLE: Phase 2A Study Evaluating a Chemokine-Modulatory Regimen in Patients with Colorectal Cancer Metastatic to the Liver

avoided per the interventional radiologists' discretion. Any biopsy core which appears as necrotic should be discarded.

Label the samples with study-specific subject ID number, clinical study number, protocol time point and, protocol day. Phosphate-Buffered saline, will be supplied by [name] lab and sample will be kept at ambient temperature. Samples in Dulbecco's Phosphate-Buffered Saline will be sent to [name] lab upon completion of processing (preferably ASAP within 2 hours of collection, but within 4 hours of collection is allowed). Once the remaining core has been processed to FFPE block, it will be delivered to OmniSeq

- The changes in the ratio between CTL marker (CD8a gene expression) to Treg markers (FoxP3 gene expression), using RT-PCT will be considered as a primary endpoint of efficacy.

Additional correlative studies may be performed on the same material:

- Comparison (using RT-PCR, Immunofluorescence [IF] and immunohistochemistry [IHC] on serial sections) of the metastatic tissue specimen with regard to total numbers of infiltrating T cells, their CD4/CD8 ratios, frequencies of FoxP3 cells, and the expression of chemokine receptors on CD4⁺ and CD8⁺ T cells (CXCR3, CCR5, CCR4, CCR6, and CXCR4).
- Evaluate the local expression of T_{eff}-attracting chemokines (CCR5, CXCL9, CXCL10 and CXCL11) and T_{reg}-favoring chemokines (CCL22 and CXCL12) using IF and RT-PCR.
- Additional tissue evaluations, including OmniSeq Immune Report card, NanoString or similar, may be performed, depending on the availability of funding.

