19 STATISTICAL PLAN

19.1 Study Design/Endpoints

This is a Phase 2A study of the chemokine-modulating regimen Celecoxib, IFN α , and rintatolimod. The regimen will be evaluated via serial biopsies comparing the quantity of tumor infiltrating CD8+ cells prior to therapy with that seen post-therapy. Tumor imaging will be repeated at day 46 (+/- 3 days) to assess objective response to therapy. Tumor infiltrating CD8+ cells in the biopsied tumor will be measured by quantitative RT-PCR and results will be expressed as a ratio to a housekeeping gene.

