19.2 Power and Sample Size

Sample Size Determination: We consider a five-fold increase in TIL expression as clinically meaningful. In a series of 55 *ex-vivo* CRC tumor specimens from patients treated surgically for recurrent CRC, the log (base 10) transform of the TIL expression yielded an estimated mean = 1.2

PROTOCOL TITLE: Phase 2A Study Evaluating a Chemokine-Modulatory Regimen in Patients with Colorectal Cancer Metastatic to the Liver

and standard deviation = 0.9. A fivefold increase due to chemokine modulation would increase the mean from 1.2 to 1.9 (a 0.77 SD shift).

The sample size calculations are based on the primary analysis, where the change in TILs is evaluated using a one-sided permutation t-test. With a sample size of n=12 *evaluable patients*, the study design has 90% power to detect a 0.77 standard deviation increase (pre- to post-treatment) at a significance level of 0.1. Therefore we have an adequate design to detect a clinically meaningful increase in TIL expression.

Analysis Cohorts and Patient Replacement: Patients missing pre-treatment and/or post-treatment TILs are considered unevaluable for the primary endpoint, and will be replaced. Patients that receive at least one study dose will be included in the *safety analysis cohort*. Patients that are considered ‘evaluable’ for the primary endpoint will be included in the *primary analysis cohort*. All patients that receive at least one study dose and are followed for clinical outcomes will be included in the *secondary analysis cohort*.

Demographics: Patient characteristics will be summarized for each analysis cohort using the appropriate descriptive statistics – mean, standard deviation, and percentiles for continuous variables; and frequencies and relative frequencies for categorical variables.

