19.3 Proposed Data Analysis

Primary Analysis: The *primary objective* is to determine the impact of a chemokine-modulatory regimen on the immune microenvironment of colorectal liver metastases. The *primary endpoint* is the change in TILs, as measured by CD8= transcript, which is treated as a continuous variable.

The TILs will be summarized by time-point (pre-/post-treatment) using the mean, median, standard deviation; and graphically using dot-plots. A 90% confidence interval for the mean change in TILs will be obtained using standard methods. Using a one-sided permutation paired t-test, the following hypotheses about the change in TILs will be evaluated:

$$H_0: \mu_d \leq 0 \text{ versus } H_A: \mu_d > 0,$$

where μ_d is the true change in TILs (post-treatment – pre-treatment).

This analysis will be limited to subjects who are considered evaluable for efficacy. Therefore the recommended sample size for efficacy is 12 *evaluable subjects*.

Secondary Analysis: The secondary objectives are to evaluate the clinical outcome of objective response and safety of the proposed therapy. The responses (based on RECIST v1.1 criteria) will be treated as binary data and summarized using frequencies and relative frequencies; with the objective response rate (ORR) estimated using a 90% confidence interval obtained using Jeffrey’s prior method. The safety analysis is described in Section 9.4.

Exploratory Analyses: The exploratory objectives are to evaluate the clinical outcomes of overall survival (OS) and progression-free survival (PFS). The OS and PFS will be treated as bivariate time-to-event data and will be summarized using standard Kaplan-Meier methods. OS will be defined as the time from the start of treatment until death due to any cause or last follow-up. PFS will be defined as the time from the start of treatment until disease progression (defined by RECIST 1.1) or last-follow-up.

PROTOCOL TITLE: Phase 2A Study Evaluating a Chemokine-Modulatory Regimen in Patients with Colorectal Cancer Metastatic to the Liver

Interim Analysis: As part of amendment #8, an interim analysis will be utilized to examine whether refinement of patient selection (i.e. earlier line) and tumor selection (i.e. selection of lesion and number of tumor cores) will improve: 1) the intra-subject variability observed in the first patients (likely due to choice of lesion and abundance of necrotic tissue), and efficacy with respect to the primary end-point (change in TILs).

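### The stated primary objective is the change in CD8a/FoxP3, but the plan sizes, tests and monitors CD8 alone, so the ratio has no prespecified analysis

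*Combined protocol and SAP*

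**What the plan says.** Two places name the CD8a/FoxP3 ratio as primary:

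- Section 1.1.1 asks for the effect on the tumour immune microenvironment, "specifically the changes in the ratio between CTL marker (CD8a gene expression) to Treg markers (FoxP3 gene expression").
- Section 11.3 says of the change in the same ratio that it "using RT-PCT will be considered as a primary endpoint of efficacy" (RT-PCT presumably means RT-PCR).

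The endpoint and statistical sections use CD8 without FoxP3:

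- Section 8.1 defines the primary endpoint through CD8, "measured as the ratio between the CD8 mRNA message and the expression of the housekeeping gene HPRT".
- Section 19.1 says CD8+ cells "will be measured by quantitative RT-PCR and results will be expressed as a ratio to a housekeeping gene", without naming the gene.
- Section 19.2 sizes the trial on a five-fold rise in TIL expression. In 55 specimens "the log (base 10) transform of the TIL expression yielded an estimated mean = 1.2", with SD 0.9. From this, "the study design has 90% power to detect a 0.77 standard deviation increase (pre- to post-treatment) at a significance level of 0.1". The link from TIL to CD8 comes from 19.1 and 19.3.
- Section 19.3 restates the objective, which "is to determine the impact of a chemokine-modulatory regimen on the immune microenvironment of colorectal liver metastases", and stops before the ratio clause. The endpoint "is the change in TILs, as measured by CD8= transcript, which is treated as a continuous variable". The hypotheses, the interim intra-class correlation and the conditional power are all written for TILs.

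FoxP3 does not occur in Section 19. The secondary analyses there cover response and safety, and the exploratory ones cover survival and progression. Section 1.1.3 lists FoxP3 cell frequencies as a correlative, which is a different quantity from the expression ratio.

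**The concern.** The ratio will be measured by RT-PCR on the planned cores, but it has no hypothesis, test, level, SD, sample size or interval. The CD8 test cannot answer for it, because the ratio also depends on what FoxP3 does.

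This goes to the purpose of the trial. Section 2.2 describes the aim as letting effector cells in while keeping regulatory cells out, and Section 2.4 cites improved CD8/FOXP3 ratios among its earlier biologic signals. If the plan is followed, a CD8 rise could be reported as a shift in CTL/Treg balance that it does not measure.

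With two measures called primary and one analysed, the choice of which defines success also stays open after data are seen. That risk is concrete: the interim-analysis text in 19.3 refers to variability already observed in the first patients. The interim decision on whether to continue as planned or consider dose escalation also rests on TILs alone.

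**Working it through.** **1. Reproduce the stated power.** Inputs from 19.2: n = 12, one-sided level 0.1, five-fold rise, log10 SD 0.9.

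- Shift: log10(5) = 0.699, and 0.699/0.9 = 0.777. Section 19.2 prints 0.77.
- Power = P(T > t(0.90; 11 df)), where T is noncentral t with 11 df and noncentrality d√12.
- d = 0.77: noncentrality 0.77 × 3.464 = 2.667, power 0.900.
- d = 0.777: power 0.904.

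The 90% is confirmed for CD8 on log10 when the SD of the change is 0.9.

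**2. What the SD assumes.** The 0.9 is a spread between specimens. For a pre/post correlation ρ, the SD of the change is 0.9√(2(1 − ρ)), which equals 0.9 only at ρ = 0.5. The documents give no ρ, so ρ is an assumption below.

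**3. How the two measures relate.** On log10 the housekeeping gene cancels:

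change in log10(CD8a/FoxP3) = change in log10 CD8 − change in log10 FoxP3.

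- Both rise five-fold: 0.699 − 0.699 = 0. CD8 rises and the ratio does not move.
- CD8 flat, FoxP3 falls five-fold: 0 − (−0.699) = +0.699. The ratio rises five-fold and CD8 does not move.

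**4. What the CD8 test would report.** Exact sign-flip permutation test (2^12 = 4,096 patterns), n = 12, one-sided 0.1, 20,000 simulated trials per case, log10 values bivariate normal with mean 1.2 and SD 0.9. Both scales are shown because 19.2 sizes on log10 while 19.3 states no scale for the test.

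| CD8 change | Assumed ρ | Positive, log10 | Positive, raw |
|---|---|---|---|
| Five-fold rise | 0 | 0.710 | 0.562 |
| Five-fold rise | 0.5 | 0.904 | 0.705 |
| Five-fold rise | 0.75 | 0.992 | 0.857 |
| None | 0.5 | 0.102 | 0.105 |

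These rates do not depend on FoxP3. The five-fold rows apply when the true ratio change is zero, and the last row applies however much the ratio improves.

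**5. Power for the ratio.** This cannot be computed, because the documents give neither an SD for its change nor a target. As an illustration only, assuming an SD of 0.6 to 1.5 for the change in log10 ratio, n = 12 at one-sided 0.1 gives power 0.995 down to 0.607 for a five-fold change and 0.652 down to 0.270 for a two-fold change. The 90% cannot be carried over.

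**6. If both were co-primary.** Two unadjusted tests at 0.1 give a chance of at least one false positive of 1 − 0.9² = 0.19 under independence, and at most 0.1 + 0.1 = 0.20.

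**The case against.** The strongest reply is that Sections 8.1, 19.1 and 19.3 agree on CD8, and that 19.2 and 19.3 give its test, direction, level and sample size. An analyst could run the primary analysis tomorrow. On this view two sentences are out of line in a single-arm Phase 2A study of 12 evaluable patients, and rewording cures it. That is a fair account of how simple the repair can be. But one of the two sentences is the primary objective itself, and nothing in the documents says which measure governs.

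Three narrower points have merit:

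- Power of 90% at 0.77 SD holds for any roughly normal paired change. What is missing for the ratio is the SD and target that would turn 0.77 SD into a fold change.
- The equal five-fold rise is hypothetical. Section 2.5 reports suppression of a Treg-attracting chemokine in explants, which points the other way. The example shows that the measures can diverge, not that they will.
- The log10/raw gap and the dependence on correlation concern the test scale and the SD, which are related to the mismatch but separate from it.

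Section 11.3 speaks of *a* primary endpoint, so the ratio could be read as co-primary. It would still have no analysis, and there is no multiplicity rule.

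**Conclusion.** The concern stands and should be fixed before the primary analysis. Two sections make CD8a/FoxP3 primary. The endpoint definition and all of Section 19 use CD8, and no text reconciles them. Followed as written, the plan does not answer its stated primary objective.

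The contradiction needs no assumption. Its size does: with lognormal values, 19.2's mean and SD, and correlation 0.5, the CD8 test would be positive in about 90% (log10) or 71% (raw) of trials in which the true ratio change is zero because both transcripts rose five-fold. It would be positive in about 10% of trials in which only FoxP3 moved. The stated 90% power is correct for CD8 on log10 with an SD of change of 0.9; no corresponding figure for the ratio can be derived from the documents.

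**What to change.** Choose one primary endpoint and use it in 1.1.1, 8.1, 11.3 and 19.1–19.3.

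**CD8 route (cheaper, since CD8 is already sized and tested):**

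1. Reword 1.1.1 and 11.3 to *change in CD8a expression relative to HPRT, pre- to post-treatment*.
2. Name HPRT in Section 19.
3. State in 19.3 that the change is analysed on log10, the scale used for sizing.
4. Add the change in CD8a/FoxP3 to 1.1.2, 8.2 and the secondary analysis in 19.3, as an estimate with a 90% CI by the same paired log10 method.
5. State that any conclusion about CTL/Treg balance rests on that estimate and not on the CD8 test.

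Cost: an amendment with the IRB approval that 18.3 requires, and one extra paired analysis of RT-PCR data already planned. There are no further patients or samples. The route gives up a sized test of the balance.

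**Ratio route, if the sponsor wants that test:** make CD8a/FoxP3 primary and rewrite 8.1 and 19.1–19.3, with a justified SD and target for its change and a fresh sample-size calculation. The documents supply no SD, so this costs more and may change the sample size.

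Whichever is chosen, record when the choice was made and which accrued biopsy results had been seen.

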1.1.2 Secondary Objectives

- Estimate the objective response rate of a chemokine-modulatory regimen in metastatic colorectal cancer (per RECIST 1.1)
- Examine the safety and tolerability profile of the combination of Interferon Alpha-2b, rintatolimod, and celecoxib when given as chemokine modulation to colorectal cancer patients prior to surgical resection using the CTEP NCI Common Terminology Criteria for Adverse Events (CTCAE Version 4.0).

1.1.3 Exploratory Objectives

- Estimate the median progression free survival of a chemokine-modulatory regimen in metastatic colorectal cancer.
- Estimate overall survival in participants with recurrent and/or metastatic unresectable colorectal cancer who received the chemokine-modulatory regimen
- To conduct correlative science studies including:
 - Comparison (using RT-PCR, Immunofluorescence [IF] and immunohistochemistry [IHC] on serial sections) of the metastatic tissue specimen with regard to total numbers of infiltrating T cells, their CD4/CD8 ratios, frequencies of FoxP3 cells, and the expression of chemokine receptors on CD4⁺ and CD8⁺ T cells (CXCR3, CCR5, CCR4, CCR6, and CXCR4).
 - Evaluate the local expression of T_{eff}-attracting chemokines (CCR5, CXCL9, CXCL10 and CXCL11) and T_{reg}-favoring chemokines (CCL22 and CXCL12) using IF and RT-PCR.

2 BACKGROUND

2.1 Metastatic Colorectal Cancer

Cancer of the colon and rectum (colorectal cancer, CRC) is the third leading site of cancer diagnosed annually in the United States and the most common form of gastrointestinal malignancy. It accounts for approximately 150,000 new cases annually. Hepatic metastases as the sole or dominant site of life-limiting disease occur in approximately 20-50% of all patients. Median survival for patients with untreated hepatic metastases ranges from 4-12 months [1]. Complete surgical resection of isolated hepatic metastases has been demonstrated in numerous series to result in 5-year overall survival up to 58% in some series [2]. However, most patients are not candidates for resection and systemic therapy remains the mainstay of treatment. Systemic chemotherapy with

PROTOCOL TITLE: Phase 2A Study Evaluating a Chemokine-Modulatory Regimen in Patients with Colorectal Cancer Metastatic to the Liver

5-FU based regimens is associated with modest improvements in survival as compared with supportive care alone (8-14 months) [3]. The addition of oxaliplatin or irinotecan can increase survival up to 24 months. The addition of further biologic agents, including bevacizumab and cetuximab, further improves median survival to approximately 30 months [4]. However, gains in outcomes have petered off with the most recently approved agents. In the last 5 years, while three new drugs have been approved, 2 of 3 confer a median survival benefit of less than two months [5, 6]. Novel therapies and approaches are needed to alter the treatment paradigm in this disease. On the basis on compelling activity in MSI-H (micro-satellite instability-high)/MMR (mismatch repair) deficient cancer, PD-1 targeting therapy has recently been approved in MSI-H tumors and offers new hope for these patients [7]. However, MSI-H tumors represent just 3% of all stage IV colorectal cancers [8]. For the other 97%, great need remains. Therapies that might alter the tumor microenvironment and expand the therapeutic spectrum of immune checkpoint inhibitors would be practice changing.

2.2 Critical Role of the Chemokine-Driven T Cell Migration in Colorectal and Other Cancers

The numbers of effector T cells (T_{eff}) in CRC tissues have been shown to be an independent prognostic marker in CRC, with their high numbers predicting a delayed time to tumor recurrence [9-12]. In contrast, regulatory T cells (T_{reg}) in CRC patients are associated with poor tumor responses [13-16]. Chemokines and their respective receptors are critical for T cell migration and homing into tissues during homeostasis and inflammation [17-22]. Several studies have shown that chemokines are equally important for migration and homing in cancer tissues. For example, the chemokine receptors CXCR3 and CCR5 are critical for T cell entry into tumors, a process which is guided by intra-tumoral expression of their respective chemokines. High levels of the chemokine ligands for CCR5 (CCL5/RANTES) and CXCR3 (CXCL9/MIG, CXCL10/IP10, CXCL11/I-TAC) in tumor tissue have been associated with infiltration of CD8 T cells in CRC [23], malignant melanoma [24] and gastric cancer [25]. High CXCR3⁺ T cells in the peripheral circulation for example have been associated with increased survival of stage III melanoma patients [26]. In contrast, high levels of CCL22 (ligand for CCR4) expression by dendritic cells (DC) or macrophages in ovarian ascites leads to recruitment of regulatory T cells; a pattern associated with decreased patient survival [27].

As shown by the above studies, selective enrichment of T cells with specific chemokine receptors in patients with cancer may impact tumor response and patient survival. But most tumors do not have T cell infiltration or express the right chemokines for effector T cell (T_{eff}) entry. Colon tumors frequently show elevated CCL22 levels induced by a Prostaglandin E₂ (PGE₂) rich tumor microenvironment [28, 29] permitting the influx of regulatory T cells (T_{reg}) rather than T_{eff} . This leads to a highly biased and unfavorable T_{reg}/T_{eff} ratio in tumors.

This study attempts to correct the above mentioned chemokine bias in the colorectal tumor microenvironment and analyze whether such modulation can help T_{eff} entry while simultaneously preventing T_{reg} influx into tumors.

2.3 Past experience with IFN α , Rintatolimod and Celecoxib

Interferon-alpha (Intron® A) is currently FDA approved for the adjuvant treatment of stage III melanoma. It has been examined by multiple investigators as an immune modulator in the setting of vaccine therapy with demonstrated safety [30]. It has been extensively evaluated in the setting

PROTOCOL TITLE: Phase 2A Study Evaluating a Chemokine-Modulatory Regimen in Patients with Colorectal Cancer Metastatic to the Liver

of metastatic CRC (as single agent or in combination with chemotherapy or IL-2), but was shown to be largely ineffective [31-48] at daily doses ranging from 3-20 million units/m², administered subcutaneously or intravenously. In the treatment of melanoma, a small study by Astsaturov and colleagues [49] administered IFN α -2b in previously vaccinated melanoma patients, and was shown to convert immunization into objective clinical responses, suggesting its ability to amplify the effectiveness of local T cells infiltration and/or function at the tumor site. Vaishampayan et al examined IFN α -2b 5 million units subcutaneously three times a week following vaccination with a melanoma vaccine (Melaccine) [50]. Treatment at this dose was well tolerated. Similarly Mitchell et al recently completed a large trial examining IFN α -2b, 5 million units subcutaneously three times a week for one year [51]. Di Pucchi and Pilla similarly examined the combination of a melanoma peptide vaccine with IFN α -2b, 3 million units subcutaneously three times a week, with little to no toxicity.

We propose to include a short course of high dose Interferon Alpha-2b (20 million units/m², IV, daily for 3 days), a dose similar or lower than the previously evaluated dose in melanoma patients [52-54]. In this group of patients, in accordance with previous reports, we expect to consistently observe flu-like symptoms but no regimen limiting toxicities, particularly taking into account the short duration of this administration.

Celecoxib has been extensively studied in long term clinical trials in patients predisposed to the development of colorectal cancer [55, 56]. However, there is to our knowledge, no clinical data examining its use as a short term immune modulator in the setting of neoadjuvant therapy. Several studies in murine models have suggested improved efficacy of anti-tumor vaccination with Cox-2 inhibition [57-59]. Recent literature suggests increased risk of adverse cardiovascular events associated with the administration of some selective Cox-2 inhibitors [60-62]. The literature regarding the precise risk with celecoxib remains controversial, with reported cardiovascular side effects observed mainly in long-term users. It has been suggested that lower doses and shorter lengths of administration may decrease the risk of adverse cardiovascular events. This trial will involve a short course of celecoxib, consisting of 200 mg twice a day for 3 days during administration of the chemokine modulation.

Rintatolimod (Selective toll-like receptor-3 [TLR3] Ligand; analog of poly IC with reduced toxicity for i. v. use).

Rintatolimod is a TLR3 specific Poly IC analog in which the cytidylic acid chain has uridylic acid substitutions at a molar ratio of 12:1. Chemokine modulation in temporal association with type I interferon administration is observed with this agent.

Rintatolimod has been studied extensively in multiple clinical settings including cancer, chronic viral infection, vaccination protocols, and in chronic treatment of chronic fatigue syndrome.

Rintatolimod (Ampligen[®]) has been generally well tolerated with only a low incidence of clinical toxicity. Clinical experience with Rintatolimod now totals over 800 patients with more than 200 patients receiving Rintatolimod for up to one (1) year, over 50 patients up to two (2) years, and more than 20 patients over two (2) years.

The proposed dosage of 200 mg IV is the starting dose used in chronic treatment of Chronic Fatigue Syndrome (CFS). That dose is escalated to 400 mg IV twice weekly for the CFS indication; however for use as a chemokine modulator, pharmacologic peak serum levels are achieved at 200 mg; thus, 200 mg daily for 3 days will be incorporated for the immune modulation regimen.

PROTOCOL TITLE: Phase 2A Study Evaluating a Chemokine-Modulatory Regimen in Patients with Colorectal Cancer Metastatic to the Liver

[figure not shown]
Preclinical evidence demonstrates the synergy between IFN α and Rintatolimod in inducing the production of the effector T cell-attracting chemokines.

2.4 Clinical experience with Rintatolimod (Ampligen®) in combination with Interferon Alpha-2b and Celecoxib.

NCT01545141 (UPCI 10-131) was a phase I study which evaluated the combination of rintatolimod, interferon-Alpha 2b, and Celecoxib administered for one course over 5 days, prior to tumor resection. The phase I study was completed, with escalation to the maximal planned dose, without the emergence of undue toxicity. A 5 day regimen consisting of rintatolimod 200 mg IV daily, Interferon Alpha-2b (20 million units/ m²) IV daily and celecoxib 200 mg po bid was deemed tolerable and suitable for further investigation.

In addition to the demonstrated safety, preliminary evidence of biologic efficacy was observed. Individuals who were treated with CKM prior to resection, demonstrated an improvement in intratumoral CD8/FOXP3 ratios as well as CXCL10/CCL22 ratios when compared to nonrandomized controls, treated with standard care at the University of Pittsburgh. The design (neo-adjuvant treatment) and numbers of patients treated do not permit any meaningful estimate of clinical outcomes or radiographic response at this time.

NCT01545141: Improved Patterns of ***Intratumoral Chemokines and T Cell Markers*** in 9 CKM-treated CRC Pts

In addition to the evaluation of rintatolimod, interferon Alpha-2b and Celecoxib administered i. v. for one course over 5 days, as a stand-alone treatment, the same combinations (but different administration regimens) are being evaluated as a part of combinatorial regimens in additional patients with peritoneal carcinomatosis (NCT02151448 / UPCI 12-110) and recurrent ovarian cancer (NCT02432378 / UPCI 11-128). Clinical trial NCT02151448 (over 50 patients evaluated

PROTOCOL TITLE: Phase 2A Study Evaluating a Chemokine-Modulatory Regimen in Patients with Colorectal Cancer Metastatic to the Liver

so far) involve multiple cycles of DC vaccines followed by 4 day long cycles of IFN- α /celecoxib regimen, with rintatolimod administered on days 2 and 4 of each cycle). Clinical trial NCT02432378 (5 patients evaluated so far) involve multiple cycles of intraperitoneal (i.p.) chemotherapy followed (with 1 day delay) with single i.p. doses of rintatolimod (with increasing i.p. doses of IFN α and a standard dose of celecoxib (orally).

No DLTs have been observed in either of these trials.

